7. ADVERSE EVENTS

An AE is any untoward medical occurrence in a patient or clinical investigation patient administered a pharmaceutical product that does not necessarily have a causal relationship with this treatment. An AE can therefore be any unfavourable and unintended sign (including an abnormal laboratory finding), symptom, or disease temporally associated with the use of an investigational product, whether or not related to the investigational medicinal product.

Any pre-existing conditions or signs and/or symptoms present in a patient before the start of the study (i.e., before informed consent) should be recorded as medical/surgical history. Any medical occurrences that are new or worsened from the time of informed consent and up to and including the final visit must be reported as AEs or SAEs. All AEs and SAEs must be recorded irrespective of whether they are considered drug-related.

Patients will be monitored throughout the study for adverse reactions to the study medications and/or procedures at each study visit. Questions will be posed in a non-leading manner so as not to bias the response. In addition to questioning at specific time points, patients will be encouraged to report any AEs spontaneously. Any patient with an AE, SAE or clinically significant abnormal laboratory test value will be evaluated by the Investigator, or a monitoring physician, and will be treated and/or followed up until the symptoms or values have resolved or are assessed as stable by the Investigator. A physician, either at the Investigative site or at a nearby hospital emergency room, will administer treatment of any SAEs. Where appropriate, medical tests and examinations may be performed to ensure that an AE has fully resolved.

Adverse events will be monitored throughout the study from the time a patient is consented through the final follow-up visit; SAEs are to be collected from the time of consent through to the follow-up visit. Whenever possible, a specific disease or syndrome rather than individual associated signs and symptoms should be identified by the Investigator and recorded on the patient's eCRF. However, if an observed or reported sign or symptom is not considered a component of a specific disease or syndrome by the Investigator, it should be recorded as a separate AE on the patient's eCRF.

Each AE or SAE reported will be assessed for severity and the date and time of onset (if available), time relationship to dosing, duration and outcome of each event will be noted.

Laboratory abnormalities are not considered AEs unless they are associated with clinical signs and symptoms or require medical intervention. Clinically significant abnormal clinical laboratory findings or other abnormal assessments that are associated with the disease being studied, unless judged by the Investigator as more severe than expected for the patient's condition, or that are present or detected at the start of the study and do not worsen, will not be reported as AEs or SAEs.

The Investigator will exercise medical and scientific judgment in deciding whether an abnormal clinical laboratory finding or other abnormal assessment is clinically significant.

7.1 Assessment of Severity (Intensity)

The following definitions for rating severity (intensity) will be used:

Mild: A type of AE that is usually transient and may require only minimal treatment or therapeutic intervention. The event does not generally interfere with usual activities of daily living.

Moderate: A type of AE that is usually alleviated with specific therapeutic intervention. The event interferes with usual activities of daily living, causing discomfort but the patient is still able to function.

Severe: The type of AE that interrupts usual activities of daily living, or significantly affects clinical status, or may require intensive therapeutic intervention.

7.2 Assessment of Relationship to Study Drug

The Investigator will use his/her clinical judgment to explain each AE and determine its relationship, if any, to study drug treatment. Alternative causes, such as natural history of the underlying diseases, concomitant therapy, other risk factors and the temporal relationship of the event to the study drug will be considered and investigated. The Investigator will also consult the Investigator's Brochure in the determination of his/her assessment. Causality should be assessed using the following categories:

Not Related The event could readily be explained by factors not involving the study drug and a temporal relationship with the study drug did not exist.

Possibly Related There was some temporal relationship between the event and the administration of the study drug and the event was unlikely to be explained by the patient's medical condition or other therapies.

Probably Related The temporal relationship between the event and the administration of the study drug was suggestive, and the event was less likely to be explained by the patient's medical condition or other therapies.

Definitely Related The event followed a reasonable temporal sequence from administration of the study drug, followed a known or suspected response pattern to the study drug, was confirmed by improvement upon stopping the study drug (dechallenge) and reappeared upon repeated exposure (rechallenge). (Note: this is not to be construed as requiring re-exposure of the patient, however, a category of definitely related can only be used when recurrence was observed).

7.3 Serious Adverse Events

An SAE is any untoward medical occurrence that:

- Results in death
- Is life-threatening
- Results in persistent or significant disability/incapacity

- Requires in patient hospitalization or prolongation of existing hospitalization
- Is a congenital anomaly/birth defect
- Is an important medical event

NOTE: medical or scientific judgment should be exercised in deciding whether reporting is appropriate in other situations, such as important medical events that may not be immediately life threatening or result in death or hospitalization but may jeopardize the patient or may require medical or surgical intervention to prevent one of the other outcomes listed in the above definition. These should also be considered serious. Examples of such events are invasive or malignant cancers, intensive treatment in an emergency room or at home for allergic bronchospasm, blood dyscrasias or convulsions that do not result in hospitalization or development of drug dependency or drug abuse.

All SAEs for patients occurring from the time of informed consent through to the follow-up visit must be reported to Panoptes Pharma GesmbH or their representative within 24 h of the knowledge of the occurrence (this refers to any AE that meets one or more of the aforementioned serious criteria). Reporting is done by completing the SAE form electronically in the eCRF system for the study.

The SAE form should be completed in as much detail as possible but a lack of complete information should not delay the reporting of the SAE.

There may be situations when an SAE has occurred and the Investigator has minimal information to include in the initial report to Panoptes Pharma GesmbH. However, it is very important that the Investigator always makes an assessment of causality for every event prior to transmission of the SAE report form to Panoptes Pharma GesmbH. The Investigator may change his/her opinion of causality in light of follow-up information, amending the SAE report form accordingly. The causality assessment is one of the criteria used when determining regulatory reporting requirements.

The Investigator will provide the assessment of causality as per instructions on the SAE form in the CRF.

If an SAE occurs during this study, the following (Sponsor) personnel should be contacted:

[name]:

Phone (office and after-hours): [name]

7.4 Other Reportable Events

Certain events that occur in the absence of an AE should be reported to the Sponsor as Other Reportable Events. These include the following:

- Pregnancy exposure (female partners of male patient becomes pregnant while taking study drug)
 - Although pregnancy is not technically an AE, all pregnancies must be followed to conclusion to determine their outcome. This information is important for both drug safety and public health concerns. It is the responsibility of the Investigator or designee to report any pregnancy in a patient that occurs during this study to Panoptes Pharma GesmbH or their representative.

- Accidental exposure (someone other than the study patient was exposed to study drug)
- Overdose (patient received more than the prescribed dose of study drug within a given timeframe)
- Other medication errors that potentially place patients at a greater risk of harm than was previously known or recognized (e.g., study drug was administered by an incorrect route)

8. DRUG SUPPLIES

8.1 PP-001

The active substance being investigated in this study is PP-001. Physicochemical properties are presented in the PP-001 Investigator's Brochure.

The drug product for intraocular administration is supplied by the Sponsor as a 1 mg/ml concentrate solution (PP-001 concentrate for intravitreal injection). Together with the concentrate solution, a sterile sucrose solution for dilution will be provided. A description of the unit formula of the concentrate formulation is provided in the PP-001 Investigator's Brochure.

Preparations with different concentrations of active pharmaceutical ingredient will be administered in order to achieve the desired dose escalation. The highest administered dose of PP-001 in the planned trial will be 2.1 µg and the lowest dose will be 0.3 µg. The corresponding dilution ratios for dilution of the PP-001 concentrate solution (1 mg/mL) with the dilution liquid in the hospital pharmacy are presented in Table 4.

Table 4 Dilution of the Investigational Medicinal Product in the Hospital Pharmacy

| Dilution | 1 : 47 | 1 : 82.5 | 1 : 165 | 1 : 330 |
|---|--------|----------|---------|---------|
| Concentration after dilution, mg/mL | 0.021 | 0.012 | 0.006 | 0.003 |
| Volume of PP-001 concentrate for intravitreal injection (1 mg/mL) to be diluted with 33 mL of the dilution liquid, mL | 0.7 | 0.4 | 0.2 | 0.1 |
| PP-001 dose (per 0.1 mL injected solution), µg | 2.1 | 1.2 | 0.6 | 0.3 |

A defined volume of the concentrate solution (0.1 – 0.7 mL of PP-001 concentrate for intravitreal injection [1 mg/mL]) will be added directly into the bottle containing exactly 33 mL of the dilution liquid and mixed in order to obtain the dosing solution with the desired PP-001 concentration.

The final PP-001 dosing solutions will always be injected at a volume of 100 µL.

8.1.1 Packaging and Labelling

Study drugs will be packaged and labelled in accordance with the applicable regulatory authority requirements.

8.1.2 Storage of Study Drugs

Access to all study drugs must be restricted to designated study personnel throughout the study. PP-001 will be stored between 15 and 25°C.

8.1.3 Product Accountability

The Investigator is responsible for study medication accountability, reconciliation and record maintenance. In accordance with all applicable regulatory requirements, the Investigator or designated study site personnel must maintain study drug accountability records throughout the course of the study. This person(s) will document the amount of study drug received from the supplier, the amounts dispensed to patients as well as lot numbers and expiration/retest date of study medications.

At the conclusion of the study, any unused study drug will either be returned to a Sponsor-designated recipient or destroyed at the site after discussion with the Sponsor. If no supplies remain, this will be recorded in the drug accountability section of the final monitoring report.

All unused study drug provided by the Sponsor will be retained for purposes of drug accountability. In addition, empty and partially used vials of PP-001 will be retained by the pharmacy for the purposes of drug accountability. Every effort will be made to retain used containers of PP-001 in the pharmacy for the purposes of drug accountability.

A member of the Sponsor's clinical operations staff (or designee) will check the supplies storage, dispensing procedures and records at regular intervals throughout the study.

9. STATISTICAL ANALYSIS

Statistical analyses of the primary and secondary outcomes will be conducted as outlined below. Descriptive statistics, including the numbers and percentages for categorical variables, and the numbers, means, standard deviations, medians, minimums, and maximums for continuous variables will be provided. Additional statistical analyses, other than those described in this section, may be performed if deemed appropriate. A description of the statistical analysis performed on the study data will be outlined in the Statistical Analysis Plan.

9.1 Treatment Comparison of Interest

The relationship between safety and efficacy results and exposure to PP-001 will be investigated.

9.2 Sample Size Determination

Eighteen patients will be enrolled in the study. No power calculations will be performed and the sample size is based on the requirements of the study design.

9.3 Analysis Populations

9.3.1 Intent-to-Treat Analysis Set

The Intent-to-treat (ITT) Analysis Set will consist of all patients regardless of whether or not the patient received study drug.

9.3.2 Per-protocol Analysis Set

The Per-protocol (PP) Analysis Set will consist of all ITT Analysis Set patients who have no major protocol deviations and who complete the study up to the end of the post-study assessments.

9.3.3 Safety Analysis Set

The Safety Analysis Set will consist of all randomized patients who receive any amount of study drug. All safety analyses will be conducted in this population.

9.3.4 Pharmacokinetic Analysis Set

All patients who receive any amount of study drug will be included in the formal analysis of pharmacokinetic parameters providing they have at least one evaluable pharmacokinetic sample.

9.4 Criteria for Evaluation

9.4.1 Safety Analysis Variables

Safety and tolerability of PP-001 as measured by treatment-emergent AEs (TEAEs) and vital signs.

9.4.2 Pharmacokinetic Analysis Variables

The concentration of PP-001 in plasma at Screening, 4 h \pm 1 h after dosing and on Day 2.

9.4.3 Efficacy Analysis Variables

The improvement of inflammation – or any other parameter – as shown by ophthalmic examination.

9.5 Demographic and Baseline Characteristics

Enrolment, protocol deviations and discontinuations from the study drug and the study will be summarized. Demographics (age, race, ethnicity and sex), medical and surgical history and study drug administration will also be summarized by treatment group.

9.6 Safety Analysis

Safety will be evaluated in the Safety Analysis Set by presenting summaries of AEs and vital signs.

Summary tables will be provided for all TEAEs. A treatment-emergent AE is defined as an AE with a start date and time on or after the first dose of study drug. Adverse events will be coded using the Medical Dictionary for Regulatory Activities (MedDRA®). The number and percentage of patients with TEAEs will be tabulated by system organ class and MedDRA Preferred Term for each treatment group and by severity and relationship to treatment.

Adverse events leading to premature discontinuation from the study drug and serious TEAEs will be presented either in a table or a listing.

Descriptive statistics of vital signs and the change from baseline for each scheduled evaluation will be summarized at each study visit and the worst overall post-baseline value will be provided. The number and percent of patients with treatment-emergent values with potential clinical significance will be tabulated.

9.7 Pharmacokinetic Analyses

The concentration of PP-001 in plasma will be measured in blood samples taken at Screening, 4 h \pm 1 h after dosing and on Day 2.

9.8 Efficacy analysis

All efficacy endpoints will be presented in terms of descriptive statistics.

The relationship between the change from baseline of an efficacy endpoint and exposure to PP-001 will be investigated.

9.9 Handling of Missing Data

Missing values will not be imputed.

9.10 Interim Analysis

The results from each dosing day of the first cohort will be reviewed before progressing with the subsequent dosing day. The next cohort will only commence with dosing after the previous cohort has completed all study sessions up to day 28 and no safety issues have been identified after being reviewed by the SDMB.

After a total of 12 patients have been treated in the three cohorts and after all patients have finished the last follow-up, an interim analysis by the SDMB will be conducted to identify potential safety issues and to determine the highest tolerable dose. If no safety issue can be identified, then a fourth dose with a higher amount of PP-001 will be given to Cohort 4 comprising of four patients. The dose for a potential Cohort 4 will be defined after completion of Cohorts 1 to 3.

If safety issues have been identified in any of Cohorts 2 to 4, then two-additional patients will receive the next lower dose.

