- Cohort 2 will receive 0.6 µg of PP-001
- Cohort 3 will receive 1.2 µg of PP-001

The patients within a cohort will be dosed consecutively with a minimum time interval of 7 days between the start of injection of the previous patient and start of injection of the next patient. The results from each dosing day will be reviewed before progressing with the subsequent dosing day. The next cohort will only commence with dosing after the previous cohort has completed all study sessions up to Day 28 and no safety issues have been identified after being reviewed by the safety data management board (SDMB).

After 12 patients have been treated in the three cohorts and after all patients have finished the last follow up an interim analysis by the SDMB will be conducted to identify potential safety issues and to determine the highest tolerable dose. If no safety issue can be identified, then a fourth, higher dose will be given to a cohort of four patients (Cohort 4). The dose for a potential Cohort 4 will be 2.1 µg of PP-001.

If safety issues are identified in any of Cohorts 2, 3 or 4, two additional patients will receive the next lower dose.

Statistical Considerations:

- Sample Size: Eighteen patients will be enrolled in the study. No power calculations will be performed and the sample size is based on the requirements of the study design.
- Treatment Comparison of Interest: a comparison will be made between the cohorts with regard to safety tolerability and efficacy.

Interim Analysis: the results from each dosing day of the first cohort will be reviewed before progressing with the subsequent dosing day. Dosing of the next cohort will only commence after the previous cohort has completed all study sessions up to Day 28 and no safety issues have been identified after being reviewed by the SDMB.

Analysis Populations

- *Intent-to-treat (ITT) Analysis Set*: all patients regardless of whether or not the patient received study drug
- *Per-protocol Analysis Set*: all ITT Analysis Set patients who have no major protocol deviations, and who complete the study up to the end of the post-study assessments
- *Safety Analysis Set*: all patients who receive any amount of study drug. All safety analyses will be conducted in this population

- *Pharmacokinetic Analysis Set:* all patients who receive any amount of study drug will be included in the formal analysis of pharmacokinetic parameters providing they have at least one evaluable pharmacokinetic sample

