Variables for Analysis:**Primary**

- Safety parameters (i.e., changes in clinical signs and symptoms from ophthalmic exam, and AEs)

Secondary

- Improvement of inflammation or of any other parameter determined at the ophthalmic examination following the injection of PP-001
- The concentration of PP-001 in plasma at Screening, 4 h ± 1 h after dosing and on Day 2

Safety analysis

The incidence of treatment-emergent adverse events (TEAEs), SAEs, deaths and discontinuations of study drug due to an AE or SAE will be summarized by System Organ Class and Preferred Term according to the Medical Dictionary for Regulatory Activities, by relationship to study drug, and by severity. The incidence of potentially clinically significant vital signs will be summarized.

Pharmacokinetic analysis

The concentration of PP-001 in plasma will be measured in blood samples taken at Screening, 4 h ± 1 h after dosing and on Day 2.

Table 1. Schedule of Assessments and Procedures

| Phase | Screening | Baseline ⁱ | Pre injection | Post injection | Telephone call ^a | Safety visits | | | | | Telephone call ^a |
|--|------------------|-----------------------|---------------|------------------|-----------------------------|---------------|-----------|------------|------------|-------------------------|-----------------------------|
| Day | -14 up to dosing | -7 up to dosing | 0 | 0 | 1 | 2 | 7 +/-1 | 14 +/-1 | 21 +/-1 | 28 ^h +/-1 | 40 |
| Electroretinography | | X | | | | | | X | | X | |
| Fluorescein angiogram | X | | | | | | | | | X | |
| Optical coherence tomography | | X | | | | X | X | X | X | X | |
| Best corrected visual acuity (ETDRS) | X | X | | | | X | X | X | X | X | |
| Visual field (computerized, 30°) | | X | | | | | X | | | X | |
| Visually evoked cortical potential | X | | | | | | | | | X | |
| Intraocular pressure | X | X | | X ^b | | X | X | X | X | X | |
| Slit lamp examination ^c | X | X | X | X ^b | | X | X | X | X | X | |
| Dilated fundoscopy ^d | X | X | | X ^b | | X | X | X | X | X | |
| Study drug injection | | | | X | | | | | | | |
| Blood sampling for PK analysis | X | | | X ^{b,e} | | X | | | | | |
| Corneal endothelial microscopy | | X | | | | | X | | | X | |
| Fundus photography | | X | | | | | | | | X | |
| Amsler grid | | X | | | | X | X | X | X | X | |
| Medical and ophthalmic histories | X | X | | | | | | | | | |
| Vital signs ^f | X | X | X | | | X | X | X | X | X | |
| Twelve-lead electrocardiogram | X | | | | | | | | | X | |

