3. STUDY DESIGN

This prospective, multi-centre, open-label, non-randomized, consecutive study will be conducted in accordance with the European Union (EU) Clinical Trial Directive 2001/20/EC and 2005/28/EC, The Medicines for Human Use (Clinical Trials) Regulations 2004 and current amendments, the Declaration of Helsinki (revised version of Edinburgh, Scotland 2000), Good Manufacturing Practice (GMP), Good Clinical Practice (GCP) and the current national regulations and guidelines, approved by both the local ethics committee and regulatory authority.

Eighteen patients older than 18 years of age will be enrolled and receive a single intravitreal injection of PP-001. Patients must have chronic, posterior uveitis, intermediate uveitis or panuveitis requiring treatment and have been receiving an adequate therapy of e.g. systemic corticosteroid treatment or immunosuppressive therapy (e.g. azathioprine, methotrexate, cyclosporine, mycophenolate, tacrolimus) or any combination thereof. Any systemic therapy at study start should *be continued throughout the study*. Patients must have best-corrected Early Treatment Diabetic Retinopathy Study (ETDRS) visual acuity of 10 letters or better

(approximately 1/35 or 0.032) but equal or less than 50 letters (approximately 20/100 or 0.2) in the study eye.

Patients must give written consent for the study before any study assessments are performed. Screening assessments will be performed 8–14 days before dosing. Baseline assessments will be performed no more than 7 days before injection. The study will involve eight study visits (Screening, Baseline, the day of injection (Day 0) and Days 2, 7, 14, 21 and 28) and telephone calls on Day 1 and Day 40.

Patients will be divided into three cohorts of four patients. Patients will receive the following treatments administered as a single intravitreal injection:

- Cohort 1 will receive 0.3 µg of PP-001
- Cohort 2 will receive 0.6 µg of PP-001
- Cohort 3 will receive 1.2 µg of PP-001

The patients within a cohort will be dosed consecutively with a minimum time interval of 7 days between the dosing of the previous patient and the dosing of the next patient. The results from each dosing day will be reviewed before progressing towards the subsequent dosing day. The next cohort will only receive PP-001 after the previous cohort has completed all study sessions up to Day 28 and no safety issues have been identified after reviewed by the Safety data management board (SDMB).

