3.1.1 Dose Rationale

PP-001 will be developed for the treatment of non-infectious posterior uveitis.

For evaluation of a safe human starting dose, a calculation based on a mg/kg basis is not considered appropriate for intravitreally administered drugs. However, in the EU there is no applicable guidance available in this regard and thus, reference is made to the Food and Drug Administration's *Note for Guidance Estimating the Maximum Safe Starting Dose in Initial Clinical Trials* [Food and Drug Administration, 2005]. For PP-001, the starting dose was evaluated by normalization the compartmental volumes and concentrations of the therapeutic doses between rabbits and humans. Using the different volumes for vitreous humour (rabbit and human) the NOAEL dose of 10 µg/eye in rabbits would therefore correspond to a human dose of 26.7 µg/eye.

Since this study will involve patients data on the minimum efficacious dose of PP-001 and its exposure in vitreous and retinal tissues (which are both considered the main target tissues) are considered. More importantly, this calculation provides an additional safety margin compared to a simple normalization based on differences in the size of eyes (rabbit vs. human) and is to be preferred because of the steep dose-toxicity curve that was observed in the intravitreal toxicity study in rabbits.

An oral dose of 25 mg/kg was shown to be efficacious in the EAU rat model. This dose level led to an ocular AUC of 1.27 µg·h/g and 4.8 µg·h/g for vitreous and retina in pigmented animals, respectively. Exposure of vitreous and retina have been determined after intravitreal injection of various doses of PP-001 into pigmented rabbit eyes. By applying a linear extrapolation it was calculated that an efficacious dose of approximately 0.25–0.36 µg/eye in rabbits corresponds to an efficacious retinal AUC of 4.8 µg·h/g, whereas a dose of 0.20–0.27 µg per rabbit eye is needed to reach an efficacious vitreous AUC of 1.27 µg·h/g (see Table 2).

Considering the higher vitreous volume of the human eye, a dose of 0.54 to 0.96 µg/eye is expected to achieve efficacious exposure in the human vitreous and retina, respectively.

Table 2 Calculated Human Efficacious Exposure and Dose

| Species | Vitreous humour [ml] | Efficacious dose based on exposure in retina | Efficacious retinal AUC (µg·h/g) | Efficacious dose based on vitreous Exposure | Efficacious vitreous AUC (µg·h/g) |

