3.2 Potential Risks and Benefits to Human Patients

PP-001 is a novel chemical molecule to inhibit a known enzyme called DHODH, a known drug target for systemic treatment of rheumatoid arthritis, psoriatic arthritis and multiple sclerosis. PP-001 is a novel inhibitor of DHODH and has the potential to deliver a new treatment for patients with severe non-infectious uveitis. Currently patients suffering from intermediate and/or the posterior uveitis (i.e., the vitreous body and retina/choroid are affected) are routinely treated with systemic corticosteroids with well known side effects. The future expected therapeutic role of PP-001 will be as a steroid-sparing agent that will allow steroid doses to be tapered quickly or even replaced.

In this proposed study the safety and tolerability of single doses of intravitreally administered PP-001 will be evaluated. Based on the preclinical pharmacokinetics the ocular half-life is

expected to be less than 20 h and the systemic exposure is expected to be below the biological activity and close to or below the limit of detection of the applied bioanalytical method (10 ng/ml). Due to the local treatment (intravitreal injection) and the preclinical data on plasma exposure of PP-001 it is unlikely that there will be any systemic exposure of PP-001 in human and therefore no systemic effects of PP-001 are expected.

This study will identify the tolerated doses at expected efficacious ocular exposures and will serve as the basis for further studies long term acting PP-001.

The inclusion and exclusion criteria restrict access to the study to severely affected patients with severely compromised visual acuity

At this stage of development, toxicity of PP-001 in human eyes cannot be ruled out but the risk is considered low based on the safety factor calculated using preclinical data. Considering the expected low systemic exposure of PP-001, potential systemic side effects known from other DHODH inhibitors are not expected. In order to minimize this risk, the first patient will receive the lowest dose, which is approximately 90 times less than the established safe concentration in preclinical studies. The next patient will only receive an injection after a safety gap of 7 days and review of all data by the SDMB. The next highest dose will only be administered after the safety of the lower dose has been established.

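### The 7-day dosing gap lets the next patient be injected before the previous patient's Day 7 visit, and section 9.10 words the review rule for Cohort 1 alone

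*Protocol*

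**What the plan says.** **Spacing.** Protocol section 3 requires "a minimum time interval of 7 days between the dosing of the previous patient and the dosing of the next patient". The synopsis gives the same interval, counted from start of injection to start of injection.

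**Visit window.** Table 1 schedules the Day 7 visit with a tolerance of one day either way. Among the tests first repeated there is "Corneal endothelial microscopy"; the computerized visual field is the other.

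**Review before the next patient.** Section 3.2 is the most demanding statement: "The next patient will only receive an injection after a safety gap of 7 days and review of all data by the SDMB". It does not list which visits make up the data. Section 10.2 refers to an SDMB policy for details, and that policy is not among the documents.

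**Review before the next dosing day.** Section 3 says "The results from each dosing day will be reviewed before progressing towards the subsequent dosing day". The synopsis design text, section 5.2.2 and SAP 3.1 say the same in almost the same words: "The results from each dosing day will be reviewed before progressing with the subsequent dosing day". None of these limits the rule to a cohort, and none names the reviewer. Section 9.10 and the synopsis entry on interim analysis add a limit: "The results from each dosing day of the first cohort will be reviewed before progressing with the subsequent dosing day".

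**The concern.** This is a first-in-human study, and patients within a cohort are injected one at a time so that each eye informs the decision to treat the next. That works only if the results meant to inform the decision exist when it is made. A 7-day gap followed by a Day 7 visit looks designed so that the visit comes first. As written, the order is not fixed, because the gap is an exact minimum and the visit has a window around the same day.

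If the visit falls late, the next eye can be injected when nothing after the Day 2 visit is in hand for the previous one. The visual field and the corneal endothelium would then not have been examined since before injection.

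The cohort limit in section 9.10 raises a second, smaller question: whether the review before each dosing day is meant to apply above the lowest dose.

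**Working it through.** **1. Calendar.** Section 6 defines injection as 0 h on Day 0.

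- Earliest next injection: 0 + 7 = Day 7 of the previous patient.
- Permitted days for the Day 7 visit: 7 − 1 to 7 + 1, so Day 6, 7 or 8.
- Visit day minus earliest injection day: −1, 0 or +1.

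A Day 6 visit comes first. For a Day 7 visit the order within the day is not set. A Day 8 visit comes one day after the earliest next injection.

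**2. What has been repeated by then.** Table 1 has 12 ophthalmic tests. Each is placed at its first post-injection time point:

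| First repeated | Tests | Number | Running total |
|---|---|---|---|
| By Day 2 | OCT, visual acuity, intraocular pressure, slit lamp, dilated fundoscopy, Amsler grid | 6 | 6 |
| Day 7 | Visual field, corneal endothelial microscopy | 2 | 8 |
| Day 14 | Electroretinography | 1 | 9 |
| Day 28 | Fluorescein angiogram, visually evoked potential, fundus photography | 3 | 12 |

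At the earliest next injection, 6 of 12 tests have been repeated if the visit falls on Day 8, and 8 of 12 if the visit is already complete.

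**3. Does section 3.2 close the gap?** It sets two conditions, the 7-day gap and SDMB review of all data. A review held on Day 7 can cover only what exists on Day 7. If the visit is booked for Day 8, a board that has seen everything collected so far can reasonably consider the condition met. The text permits waiting for the visit but does not require it.

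**4. Exposure during the gap.** Section 3.2 expects an ocular half-life under 20 h. Seven days is 7 × 24 = 168 h, and 168 / 20 = 8.4, so at least 8.4 half-lives. At the top of the rabbit range in section 1.3.2 (21 h) it is 168 / 21 = 8.0. Little drug should remain by Day 7, which limits the concern but does not supply the missing results.

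**5. Scope of the review rule.** Two places carry the cohort limit: section 9.10 and the synopsis interim analysis entry. Five do not: the synopsis design text, sections 3, 3.2 and 5.2.2, and SAP 3.1. Reviewing before every dosing day in every cohort satisfies all seven. The narrower sentences are incomplete restatements and do not contradict the others.

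**6. Time cost of requiring the visit.** Let r be the days from visit to next injection. The step then lasts 6 + r to 8 + r days, against 7 now.

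- r = 1: (6 + 1) − 7 = 0 to (8 + 1) − 7 = 2 days added per step.
- r = 3, an assumed review time since the documents give none: 2 to 4 days added per step.
- Steps: SAP 4.8 closes the study at Cohort 3, so 3 cohorts × (4 − 1) = 9.
- Total: 0 to 18 days for r = 1, and 18 to 36 days for r = 3.
- Shortest escalation under the present rule: 3 × (3 × 7 + 28) = 147 days, or 3 × (21 + 27) = 144 days if each cohort's last Day 28 visit falls on Day 27.
- Upper limits: 18/147 = 12.2% to 18/144 = 12.5% for r = 1; 36/147 = 24.5% to 36/144 = 25% for r = 3.

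**The case against.** The case against the timing point is substantial. Seven days is a minimum, section 3.2 adds SDMB review, and the board may wait for the Day 7 visit under the present text. Its policy may already say so. The rabbit toxicity at 20 and 30 µg per eye was in retina, choroid and vitreous (section 1.3.3), and OCT, fundoscopy, slit lamp and acuity, all repeated by Day 2, examine those tissues or their function. There is also a 4-hour hospital stay with emergency vitrectomy available, a Day 1 call, ongoing medical monitoring, and stopping or dose reduction after a single related serious event (section 6.14.3). Finally, Day 7 is a choice: four of the 12 tests would still be outstanding after it.

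Most of this stands, and it lowers the severity. It does not remove the gap. Stopping rules and monitoring act on results that exist, and cannot act on a test not yet repeated. Day 7 is a sensible cut-off because the visit is already scheduled next to the permitted injection day, whereas waiting for electroretinography on Day 14 would about double the interval.

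Two stronger readings are tempting, and the documents support neither:

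- **That section 9.10 exempts Cohorts 2 and 3 from review.** A reader might add that these doses have less margin. Section 3.1.1 says the rabbit no-adverse-effect dose "would therefore correspond to a human dose of 26.7" µg per eye, so the margins are 26.7/0.3 = 89, 26.7/0.6 = 44.5 and 26.7/1.2 = 22.25. But section 9.10 exempts no cohort, and the sections on design and drug administration state the rule without limit. The margins describe no actual loss of protection.
- **That one injection in three would precede the visit.** Three visit days are permitted, but nothing says how often each is used, or how often the next injection is given at the minimum interval.

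**Conclusion.** The timing gap in the written rule is real. In the worst permitted case the next eye is injected one day before the previous patient's Day 7 visit, with 6 of 12 ophthalmic tests repeated instead of 8; the two outstanding are the visual field and corneal endothelial microscopy. This is something the schedule permits, and the documents do not show that it would happen. It requires injection at or close to the 7-day minimum, a visit on Day 8 or late on Day 7, and no stricter rule in the SDMB policy.

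The cohort limit in section 9.10 and the synopsis is a minor wording misalignment.

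Taken together this is a cheap improvement of low to moderate severity. Confidence is moderate, mainly because the SDMB policy could not be checked.

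**What to change.** In the synopsis and sections 3, 5.2.2 and 9.10, state one rule consistent with section 3.2:

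*Within every cohort, the next patient is injected no earlier than 7 days after the previous patient and only after the SDMB has reviewed all available data, including the previous patient's completed Day 7 visit.*

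If the SDMB policy already requires this, cite it there instead. In section 9.10 and the synopsis interim analysis entry, delete the words *of the first cohort*. The Day 28 rule between cohorts and the stopping criteria stay as they are.

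The wording deletion costs no time. Waiting for the visit lengthens the shortest possible escalation by at most about one eighth if injection follows one day after the visit, and by up to a quarter if it follows three days after. No visit or test is added.
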